434 to contact the subject. These attempts will include at least 1 certified mail receipt. If all attempts
435 to contact the subject fail, that subject will be considered to be lost to follow-up and discontinued
436 from the study.

437

438 *Protocol violation*: The subject's laboratory or other findings, or the subject's conduct, fail to
439 meet the protocol entry criteria or fail to adhere to the protocol requirements. Subject pregnancy
440 or intention of becoming pregnant would also be a violation.

441

442 The Stopping Criteria for individual subjects include:

443

444 The Principal Investigator, study physician, and/or nurse practitioner conclude it is unsafe for the
445 subject to continue. These reasons may include:

- 446
- 447 • A new diagnosis is made of a significant medical condition which could influence the
response to liraglutide (e.g., renal failure).
 - 448 • A medication is begun that could alter the subject's responses to liraglutide.

449

450 Subjects meeting individual stopping criteria will be withdrawn from the trial.

451

452 **Subject Replacement**

453

454 Subjects who prematurely discontinue from the study or become ineligible will not be replaced
455 once they have been randomized.

456

[figure not shown]
457 **Visit Procedures**

458

459 Figure 1 shows the flow of subjects through randomization. Table 1 presents the schedule of
460 study assessments and treatment visits.

461

462 Figure 1. Study Flow Diagram

463
464 **Screening Procedures**
465
466 All applicants will be screened by phone and questions administered through REDCap (the
467 University of Pennsylvania's research data capture system) to determine whether they potentially
468 meet eligibility criteria. We will obtain a waiver of written documentation of consent for the
469 telephone and electronic questionnaire screen. Those who appear to meet eligibility criteria and
470 remain interested in the trial will be scheduled for an in-person interview.
471

472 The in-person interview will be conducted by a psychologist or Masters' level staff member,
473 who will obtain informed consent and evaluate subjects' behavioral eligibility (i.e., willingness
474 and appropriateness to participate). Individuals who do not wish to participate in the research
475 study will receive recommendations for alternative treatments for binge eating disorder if they
476 are interested. Assessment of eligibility will include examination of the applicants' BED

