724 measures across the two treatment groups will be compared using appropriate 2-sample tests,
725 including Wilcoxon rank-sum and t-tests for continuous variables, and Fisher's exact and Pearson
726 Chi-square tests for categorical variables. Any baseline variables found to be associated with
727 treatment condition will be added to the outcome analysis as a covariate.

728
729 **Primary analysis.** The primary outcome is the degree of reduction in binge episodes per week.
730 It is count data that is likely to be skewed, so a shifted log transformation will be considered to
731 stabilize the distribution to better meet the normality assumptions. To address the primary aim 1,
732 a mixed effects model will be fit with Treatment Group (liraglutide 3.0 mg/d and placebo) as a
733 between subjects factor and Time (Weeks 1 through 17) as a categorical within-subjects factor.
734 Time is treated as a categorical factor so that we can use the group-time interactions with the
735 time main effect to estimate and test intention-to-treat (ITT) treatment group differences at each
736 time point, with the 17-week time point as our primary ITT test. In fitting a mixed effects model
737 with maximum likelihood, a variance-covariance structure must be selected. We will begin by
738 assuming a compound symmetry structure, but also consider criteria such as the Akaike's
739 Information Criterion (AIC) for selecting the best form of the variance-covariance structure
740 using Residual Maximum Likelihood (REML) (e.g., Compound Symmetry, Toeplitz, first-order
741 autoregressive, and unstructured). Furthermore, we will include as baseline covariates those
742 variables that have been established to be associated with the outcome based on prior literature,
743 including sex and age. The results from the mixed model will be summarized by mean (SE)
744 change from baseline for each treatment group at each time point.
745

746 Given the above definition of the ITT tests under the mixed effects model, the main interest in
747 this study is the to the test of the primary hypotheses that participants randomized to liraglutide
748 3.0 mg/d (N=76) will show superior improvements from baseline to treatment end (week 17) in
749 the number of binge episodes per week as compared to those on placebo (N=76). The primary
750 hypothesis will be evaluated at the alpha = 0.05 level and all other contrasts and

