751 secondary/tertiary outcomes/hypotheses will be considered exploratory and those results will be
752 interpreted with caution at alpha equal to 0.05 level. Analyses will be conducted using the
753 statistical software package, SAS for Windows (SAS Institute, Inc., Cary, NC) [48].
754

755 As a sensitivity analysis, we will alternatively use a negative binomial distribution to model the
756 rate of binge eating episodes per week (taking into account the trial duration for individual
757 subjects) and will count r as a number of binge eating episodes. The binge eating episodes per
758 week ratio will be compared between the liraglutide and placebo groups.
759

760 *Of note, the analysis plan for the primary outcome variable will remain the same, but the final
761 sample size will be 36 instead of 152.*

762
763 **Analyses for Aim 2.** To assess differences among the two conditions in the percentage of
764 participants who were in remission (2 binary outcomes), generalized estimating equation (GEE)
765 models will be fit with the same between group, within group, and interaction terms as presented
766 above, as well as, any relevant baseline covariates. A binomial distribution will be specified
767 using a logit link function, and the unstructured covariance matrix will be considered to adjust
768 for the within subject clustering of repeated measures data. From the GEE models, odds ratios
769 and 95% confidence intervals will be computed to compare the treatment groups at each time
770 point.
771

772 *Of note, this analysis will also be completed as proposed with the reduced sample.*

773 **Analyses for Aim 3.** The mixed effects model approach described for the primary analysis will
774 also be utilized to compare changes in body weight, global BED symptom improvement,
775 cognitive restraint of food intake, dietary disinhibition, perceived hunger, quality of life, and
776 depressed mood between treatment groups. Changes in these outcomes will also be summarized
777 by mean(SE) for each treatment group at each time point. If violations in the normality
778 assumption are observed, log transformations, as well as alternative distributions such as Poisson
779 and Negative binomial will be considered.

780
781 *Of note, cognitive restraint, disinhibition, and hunger will only be available for completers, so it*
782 *is unlikely that this model can be run for these variables. The other variables in this aim were*

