783 *administered at each visit and can be included in the proposed models.*

784
785 **Safety analysis.** Given the modest sample size, we will not perform safety analysis. Instead,
786 safety labs will be reviewed on an individual basis with participants to assure that they are within
787 normal limits, and these will be available in summary for publications/presentations. The details
788 for reporting SAEs to the IRB and procedures for taking action to safeguard participants are
789 described in the safety monitoring plan.

790
791 **Missing data and statistical models.** Every effort will be made to obtain follow-up data on all
792 participants randomized. Based on prior studies that we have conducted, the dropout rate by 17
793 weeks could be as high as 15%. Our maximum likelihood approach assumes that any missing
794 outcome data are missing at random (i.e., missing data, including those due to drop-out, but not
795 dependent on any previously observed outcomes or treatment assignment). With this approach,
796 we will use all data that have been collected, without regard to whether data are missing for a
797 participant at another visit, including drop-out, and without explicit imputation of missing data.
798 We will conduct sensitivity analyses to examine the impact of missing data. Details regarding
799 the sensitivity analyses will be pre-specified prior to unblinding. Furthermore, we will assess
800 whether dropout status or level of compliance is associated with treatment condition as well as
801 baseline demographic variables using appropriate 2-sample tests, including Wilcoxon rank-sum
802 and t-tests for continuous variables, and Fisher's exact and Pearson Chi-square tests for
803 categorical variables, and all findings will be reported.

804
805 Change in frequency of binge episodes per week also will be analyzed using a per protocol
806 analysis that, for liraglutide-treated participants, includes only those who were able to tolerate
807 and adhered to the full dose of liraglutide 3.0 mg.

808
809 **Interim Analysis**

810 No interim analyses are planned (in order to maintain full power for the end-of-study
811 comparisons).

812
813 **Explorative Statistical Analysis for Pharmacogenetics and Biomarkers**

814 No explorative statistical analysis for pharmacogenetics and biomarkers will be performed.

815
816 *5.20.19 Of note, due to unforeseen low response to advertising and the mis-allocation of*

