949 sequence; each subsequent subject to meet treatment criteria will be assigned the next number in
950 the sequence. This is a randomized, double-blind, placebo-controlled trial with a parallel groups
951 design.

952

953 **Breaking of Blinded Codes**

954 Unblinding of the treatment codes will occur after all data have been verified and deemed clean
955 by the data managers and statistician, and right before analysis of the data occurs.

956 The code for a particular subject may be broken in a medical emergency if knowing the identity
957 of the treatment allocation would influence the treatment of the subject or if demanded by the
958 subject. Whenever a code is broken, the staff-member breaking the code will record the time,
959 date and reason as well as his/her initials in the source documents. All codes (whether broken or
960 not) will be kept throughout the trial period. Accountability of all broken or unbroken codes
961 (hard copy or electronic) will be performed at or after trial closure.

962

963 **CONCOMITANT ILLNESSES AND MEDICATIONS:**

964 **Definitions:**

965 At trial entry (i.e., the screening visit), we will record details of any concomitant illness (i.e., any
966 illness that is present at the start of the trial) that is present and concomitant medication (i.e., any
967 medication other than the trial product(s) that is taken during the trial, including the screening
968 and run-in periods) in each subject's record. The information collected for each concomitant
969 medication will include the start date, stop date or continuing, and indication. For each
970 concomitant illness, we will record the date of onset, date of resolution or continuing. Any
971 changes in concomitant medication use will be recorded at each visit. If the change influences
972 the subject's eligibility to continue in the trial, the Sponsor will be informed.

973

974 **ADVERSE EVENTS:**

975 At each contact with subjects, study personnel will be responsive to reports of adverse events
976 with specific questioning and, as outlined in the procedures section, by physical examination.
977 The investigator will report all adverse events including serious adverse events (SAE), suspected
978 unexpected serious adverse reactions (SUSARs), serious adverse drug reactions (SADRs) (as
979 defined below) to the Data Safety and Monitoring Board established for the trial, and to the Penn

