1092 In case of suspected overdose, subjects will be instructed to call their healthcare provider
1093 immediately, as excessive intake of Saxenda may cause severe nausea and vomiting.
1094

1095 **LIABILITY AND SUBJECT INSURANCE:**

1096 During and following a subject's participation in trial, [name] and Penn Medicine will
1097 provide adequate medical care to the study subject for any study-related adverse events,
1098 including clinically significant laboratory values related to the study. This medical care for study
1099 subjects will be provided regardless of their insurance status.

1100
1101 [name] will be responsible for the conduct of the study and agrees to defend, indemnify, and
1102 hold harmless Novo Nordisk, any of its parent companies, affiliates, or subsidiaries, and their
1103 respective officers, directors, employees, agents, representatives, distributors, salespersons,
1104 customers, licensees, and end-users from and against any claim, suit, demand, loss, damage,
1105 expense or liability imposed by any third party arising from or related to: (a) any breach of
1106 sponsor-investigator's obligations or representations; or (b) sponsor-investigator's negligent or
1107 grossly negligent use or willful misuse of the study drug, the results, or services derived
1108 therefrom. This indemnification shall not apply in the event and to the extent that a court of
1109 competent jurisdiction or a duly appointed arbiter determines that such losses or liability arose as
1110 a result of Novo Nordisk's gross negligence, intentional misconduct, or material breach of its
1111 responsibilities.

1112
1113 **EVALUABILITY OF SUBJECTS:**

1114 Subjects will be excluded from data analysis in the event of pregnancy, amputation, bariatric
1115 surgery, or death. Additional criteria associated with subject censorship will be considered prior
1116 to initiating recruitment. Any censorship will be documented in case records and appropriately
1117 reported.

1118
1119 **PK and/or PD Modelling**
1120 No PK/PD modelling is planned in this trial.

1121
1122 **PREMATURE TERMINATION OF STUDY:**

1123 We believe that it is highly unlikely that the study will be terminated prematurely, given the
1124 safety of the intervention and its expected effects. Termination would be considered, however, in
1125 view of:

- 1126 • Unacceptable safety concerns of the study medication
1127 • The benefits observed do not ethically permit the trial to continue

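### The per-protocol analysis states a tolerance and adherence filter for liraglutide and none for placebo, so as written it compares a group selected after randomisation with an unselected one

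*Combined protocol and SAP*

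**What the plan says.** The final paragraph of Missing data and statistical models plans a second look at the primary endpoint variable: an "analysis that, for liraglutide-treated participants, includes only those who were able to tolerate" "and adhered to the full dose of liraglutide 3.0 mg". The restriction names one arm. It gives no cut-off for adherence and no time window.

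Other places where a placebo rule might stand do not supply one:

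- Evaluability of Subjects applies to both arms, but its events are not about tolerance or adherence: "Subjects will be excluded from data analysis in the event of pregnancy, amputation, bariatric" surgery, or death. It adds that further criteria would be considered before recruitment began and that any censorship would be documented and reported. No further criterion follows.
- Withdrawal Criteria lists protocol violation, where findings or conduct fail to "meet the protocol entry criteria or fail to adhere to the protocol requirements". This is a reason for discontinuation, not a rule for an analysis set.
- Missing data and statistical models also plans to assess "whether dropout status or level of compliance is associated with treatment condition as well as" baseline demographic variables. That describes compliance and defines no set.

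On status, Primary analysis puts the confirmatory weight on the ITT comparison, "with the 17-week time point as our primary ITT test", and states that all other contrasts and "secondary/tertiary outcomes/hypotheses will be considered exploratory and those results will be" interpreted with caution.

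**The concern.** Randomisation makes the two arms comparable as a whole. Keeping only the tolerant and adherent members of one arm breaks that comparability if those members would have had different outcomes anyway. Nothing in the design calls for a one-arm rule. Study medication(s) / devices(s) describes the same stepwise titration for active pens and placebo pens. The diary and dose counter (Subject Compliance) and the weekly count of doses taken (Randomization Visit) cover all subjects.

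At stake is how the supplementary result is read. It concerns the primary endpoint variable in a trial that ended with 36 participants instead of 152. A reader could take a favourable per-protocol difference as support for the ITT result when part of it may come from selection. The planned comparison of compliance by arm would show an imbalance but would not correct this contrast.

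The term for liraglutide-treated participants is also unclear here. The note dated 5.20.19 reports 9 participants switched to the opposite product after one box, and 4 and 2 retained after two and three consecutive boxes of the same product. The classing of those 9, and possibly of up to 9 + 4 + 2 = 15 of the 36, is not stated for this analysis.

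**Working it through.** **The plan's own figures.** The per-protocol analysis has no stated figure, so the check on inputs uses Sample Size Calculation: SD 4.1, difference 1.6, 10 assessments, ICC 0.59, two-sided alpha 0.05, power 80%.

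- Effect size: 1.6 / 4.1 = 0.39, as stated.
- Compound-symmetry factor: (1 + 9 × 0.59) / 10 = 0.631.
- Per arm: 2 × [4.1 × (1.960 + 0.842) / 1.6]² × 0.631 = 65.04, rounded up to 66, total 132, as stated.

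The SD and the difference are therefore read as the plan used them. The concern does not depend on the sample size.

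**Bias from filtering one arm.** Assume no drug effect, and a normal tolerance/adherence score with correlation r to reduction in binge episodes within the liraglutide arm. The lowest fraction p of that arm is removed. Neither p nor r is in the documents; both are assumptions.

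Bias = r × SD × φ(z_p) / (1 − p), where z_p is the p-quantile and φ the density of the standard normal.

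- p = 0.10, r = 0.2: 0.2 × 4.1 × 0.1755 / 0.90 = 0.16 episodes per week.
- p = 0.30, r = 0.3: 0.3 × 4.1 × 0.3477 / 0.70 = 0.61, which is 0.61 / 1.6 = 38% of the planning difference.
- p = 0.40, r = 0.4: 0.4 × 4.1 × 0.3863 / 0.60 = 1.06.
- r = 0: none. A negative r reverses the sign, so over p from 10% to 40% and r from −0.4 to +0.4 the range is −1.06 to +1.06.

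The correlation in the unfiltered placebo arm does not enter.

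**Against the noise.** With 36 participants and an assumed 18 per arm, p = 0.30 leaves 12.6 on liraglutide. SE = 4.1 × √(1/18 + 1/12.6) = 1.51, and 0.61 / 1.51 = 0.41 SE. The table shows 200,000 simulated trials per setting (two-sided t-test at 0.05, no drug effect, 18 per arm).

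| Filter | Mean bias | Significant in favour of liraglutide |
|---|---|---|
| None | 0.00 | 2.5% |
| Liraglutide only, 30%, r = 0.3 | 0.61 | 5.8% |
| Liraglutide only, 40%, r = 0.4 | 1.05 | 9.3% |
| Liraglutide only, 30%, r = −0.3 | −0.61 | 0.9% (5.7% favour placebo) |
| Both arms 30%, r = 0.3 in both | 0.00 | 2.5% |
| 30% liraglutide, 10% placebo, r = 0.3 in both | 0.37 | 4.2% |
| Both arms 30%, placebo r = 0 | 0.61 | 5.6% |
| Both arms 30%, placebo r = −0.3 | 1.22 | 11.0% |

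The last four rows show what a common rule can and cannot do. It removes the bias when selection works alike in both arms. It reduces the bias when fewer leave placebo under the same relation. It gives no gain, or does worse, when placebo r is zero or negative.

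**The case against.** The strongest reply is that this is a drafting matter. The sentence specifies the active arm without saying that placebo is unrestricted, and a per-protocol set ordinarily implies compliance in both arms. The analysis is supplementary and labelled exploratory. By the figures above, a common rule need not improve the contrast, since nothing in the documents tells us the placebo correlation. The illustration uses a t-test on normal data, whereas the plan fits a repeated-measures mixed model, possibly on a shifted log scale.

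Much of this stands. It limits the weight of the point and the use that can be made of the numbers. It does not supply the missing placebo rule. Intent cannot be read from the text, and an analyst who follows the text filters one arm.

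Four stronger readings are tempting and are not supported:

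- *That the one-arm rule prevents blinded pre-specification.* Breaking of Blinded Codes says "Unblinding of the treatment codes will occur after all data have been verified and deemed clean". Tolerance and adherence can be flagged and frozen for everyone before that point, and the arm label then applies the flag mechanically. What is missing is a cut-off and a commitment to fix it. The promise of pre-specification before unblinding is given for the missing-data sensitivity analyses, not for this set.
- *That the bias must favour liraglutide.* Its direction depends on a relation that the documents do not report.
- *That censored, non-completing and lost participants are already out, so the set is much smaller.* Missing data and statistical models keeps all collected data, and the dated note includes 36 participants in the proposed analyses.
- *That the data for a full-dose criterion are already in hand.* The documents record doses taken, injection counts and missed doses. They do not say that the dose level reached was recorded.

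**Conclusion.** The concern holds as a defect in a stated rule: tolerance and adherence are required of liraglutide-treated participants only, and no placebo counterpart exists in the documents. Whether this biases the result depends on an unreported relation between tolerance or adherence and outcome in the liraglutide arm. The 0.61 episodes per week, and the rise from 2.5% to 5.8% in false positives favouring liraglutide, are illustrations. They rest on an assumed 30% removed, r = 0.3, 18 per arm and normal outcomes. The primary test is untouched, so the consequence is minor to moderate. The change is worth making because the text is specific, the remedy is standard, and the contrast uses the primary endpoint variable.

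**What to change.** In Missing data and statistical models, replace the one-arm sentence with a definition that:

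1. applies one rule to both arms, whichever product was in the pen;
2. states an adherence cut-off based on the diary, dose-counter and doses-taken data collected for all subjects;
3. adds attainment of the full-dose step of the common titration only where the dose level reached was recorded, which should be confirmed first;
4. states how participants who received the wrong product are classed;
5. flags every participant before unblinding and reports exclusions by arm;
6. labels the result as a non-randomised supplementary comparison, with the ITT result remaining primary.

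The text should say that a common rule removes the asymmetry of the rule but does not guarantee an unbiased contrast, because tolerating active drug and tolerating placebo can select different people.

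The cost is a few sentences and a check of what was recorded. The downside is that some placebo participants leave an already small set. The classing of wrong-product participants must be decided openly. No dose or clinical rule changes.
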